### 9.2.2. Grading Scale for Severity of AEs

AEs are to be graded according to the standard criteria in **Appendix B and C**. The definitions provided in this section will be applied if there are no standard criteria given for that particular event.

- **Mild**: events require minimal or no treatment and do not interfere with the subject's daily activities.
- **Moderate**: events result in a low level of inconvenience or concern with the therapeutic measures. Moderate events may cause some interference with functioning.
- **Severe**: events interrupt a subject's usual daily activity and may require systemic drug therapy or other treatment. Severe events are usually incapacitating.
- **Life Threatening**: any adverse drug experience that places the subject, in the view of the investigator, at immediate risk of death from the reaction as it occurred, i.e., it does not include a reaction that had it occurred in a more severe form, might have caused death.

Changes in the severity of an AE should be documented to allow an assessment of the duration of the event at each level of intensity to be performed. Adverse events characterized as intermittent require documentation of onset and duration of each episode.

### 9.2.3. Reactogenicity

Adverse events associated with topical administration will vary based on formulation and extent of systemic absorption. Dermatology reactions from the topical patch include blisters, bruising, burning sensation, depigmentation, dermatitis, discoloration, edema, erythema, exfoliation, irritation, papules, petechia, pruritus, vesicles, or may be the locus of abnormal sensation. Other possible systemic reactions include bradycardia, apprehension, confusion, dizziness, drowsiness, paresthesia, nausea, vomiting, bruising, methemoglobinemia, weakness, and angioedema or anaphylactic hypersensitivity reactions. Also please refer to the attached package inserts.

The adverse events associated with systemic lidocaine administration may be cardiovascular, central nervous system, gastrointestinal, neuromuscular and skeletal, respiratory, or miscellaneous in nature. The majority of these reactions do not have a defined frequency of occurrence, and many will vary with route of administration and are dose-related. Cardiovascular

effects may include bradycardia, cardiac arrhythmia, circulatory shock, coronary artery vasospasm, edema, flushing, heart block, hypotension, or local thrombophlebitis. Central nervous system effects may include agitation, anxiety, apprehension, coma, confusion, disorientation, dizziness, drowsiness, euphoria, hallucination, hyperesthesia, hypoesthesia, intolerance to temperature, lethargy, loss of consciousness, metallic taste, nervousness, paresthesia, psychosis, seizure, slurred speech, and twitching. Respiratory reactions include bronchospasm, dyspnea, respiratory depression. Other/miscellaneous possible adverse events include nausea, vomiting, tremor, weakness, tinnitus, and anaphylaxis or hypersensitivity reactions. Asystole and methemoglobinemia have occurred in less than 1% of patients.

If an event has not been experienced previously and is not listed here, it will be categorized as an “Unexpected” AE.

#### *Primary Skin Irritation (PSI) Assessment*

PSI will be performed pre-dose, and at 12:00 hours (after patch removal), 24:00 hours, 39:00 and 48:00 hours. The skin site will be graded according to the following irritation grading scale:

- 0 - No evidence of irritation.
- 1 - Faint but definite erythema, no eruptions or broken skin or no erythema but definite dryness; may have epidermal fissuring.
- 2 - Moderate erythema, may have a few papules or deep fissures, moderate-to-severe erythema in the cracks.
- 3 - Severe erythema (beet redness), may have generalized papules or moderate-to-severe erythema with slight edema (edges well defined by raising).
- 4 - Generalized vesicles or eschar formations or moderate-to-severe erythema and/or edema extending beyond the area of the patches.

A CRU nurse or member of the study team will evaluate each subject for the occurrence of reactogenicity symptoms by assessing signs and reported symptoms by the subject and by reviewing the subject’s vital signs. A physical examination by the MAI will be conducted when appropriate.

#### **9.2.4. Serious Adverse Events**

A SAE is defined as an AE that results in any of the following outcomes:

- Death
- Life-threatening event
- Inpatient hospitalization (>24 hrs) or prolongation of existing hospitalization
- A persistent or significant disability/incapacity
- Any other important medical event that may not result in death, be life-threatening (any adverse drug experience that places the subject, in the view of the investigator, at immediate risk of death from the reaction as it occurred, i.e. it does not include a reaction that had it occurred in a more severe form, might have caused death), or require hospitalization, may be considered a SAE when, based upon appropriate medical judgment, the event may jeopardize the subject and may require medical or surgical intervention to prevent one of the outcomes listed above.

Additionally, the occurrence of the following reactogenicity symptoms is defined as an SAE:

- Any Grade 4 reactogenicity

### 9.3. Reporting Procedures

#### 9.3.1. Serious Adverse Events

The PI must report to the FDA Sponsor and the Research Involving Human Subject Committee (RIHSC) any unanticipated problems involving risk to human subjects or others according to 21 CFR 312.32(c)(2). Anticipated adverse events may be reported to the RIHSC in the annual report for continuing review.

However, certain adverse events must be reported to the RIHSC within 7 working days of the discovery of the event. The RIHSC defines these adverse events as including, but not limited to the following:

- An adverse event that is not expected, i.e. not listed in the informed consent document or the investigator's brochure;
- An expected adverse event that occurs at a greater frequency or duration than expected;
- Any adverse event that would require modification of the protocol and/or informed consent document.

The following procedures will occur if in the opinion of the PI, MAI or ISM the event meets the criteria of a SAE:

- All SAEs will be:
  - reviewed by a study physician
  - recorded on the appropriate AE and SAE form
  - followed by the MAI until satisfactory resolution or until the MAI deems the event to be chronic or the subject to be stable

Any AE considered serious by the PI, MAI, or ISM or which meets the aforementioned criteria must be submitted on an SAE form to the FDA at the following address:

[name]  
Branch Chief – Chemistry, Manufacturing and Controls at FDA  
FDA / CDER / Office of Pharmaceutical Quality / Office of Lifecycle Drug Product  
[contact] (Office)  
[contact] (Cell)  
[[contact]](mailto:[contact])

In addition, such events will be reported to the IRB in accordance with IRB policy. The PI will complete an SAE form within the following timelines:

- All deaths and immediately life-threatening events, whether related or unrelated, will be recorded on an SAE Form and sent by email to the FDA within 24 hours of site awareness.
- SAEs other than death and immediately life-threatening events, regardless of relationship, will be reported via email by the site within 24 hours of becoming aware of the event.

Other supporting documentation of the event may be requested by the FDA Pharmacovigilance Group and should be provided as soon as possible. All SAEs will be followed until satisfactory resolution or until the MAI deems the event to be chronic or the subject to be stable. The FDA Clinical Project Manager will be notified of the SAE by the FDA Pharmacovigilance Group. The FDA Medical Monitor will review and assess the SAE for regulatory reporting and potential impact on study subject safety and protocol conduct.

### **9.3.2. Reporting of Pregnancy**

Subjects must be of non-childbearing potential, or if of childbearing potential (as determined by the MAI or PI) must be practicing abstinence or using an effective licensed method of birth control (e.g., use hormonal or barrier birth control such as implants, injectables, combined oral contraceptives, some intrauterine devices (IUDs), condoms with spermicidal agents; or have a vasectomized partner). Female subjects will undergo serum pregnancy tests during the Screening Period. Pregnant or lactating women will be excluded from the study. If an eligible female subject has a positive urine pregnancy test on any of the procedure days, she will not be permitted to participate that day and will be discontinued from the study.

### **9.4. Type and Duration of Follow-up of Subjects after Adverse Events**

The administration of lidocaine is not anticipated to cause significant clinical problems. If a clinical problem would occur the subject will be discontinued from the study. If AEs occur, clinical judgment will be used with the results recorded as part of the PI or MAI judgment of the probability that an event is linked to the lidocaine procedure.

### **9.5. Halting Rules**

The ISM will review reports on protocol progress, side effects and AEs after each study arm. The PI will be informed of all SAE reports within 24 hours of their occurrence. All SAEs will be reported by the PI to the MAI, ISM, the University of Iowa IRB, and the appropriate FDA program officer. The PI will provide an initial SAE report within 24 hours of their occurrence to the ISM, University of Iowa IRB, and FDA program officer, or as soon as required by each entity, with a final report to follow.

Dosing will be halted and the data reviewed by the ISM if any of the following are observed:

- 3 or more subjects develop Grade 2 or higher of the major side-effects known to be related to lidocaine
- 2 or more subjects develop Grade 3 or higher of the major side-effects known to be related to lidocaine
- Any single SAE

When the study is halted then the PI, MAI, and ISM will determine whether further procedure days or study arms should be stopped, and/or if protocol or informed consent is modified.

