### **2.3. Potential Risks and Benefits**

#### **2.3.1. Potential Risks**

##### **Lidocaine topical patches:**

Topical lidocaine 5% patches are approved by FDA for use in the United States and have been used for many years; the likelihood of unexpected frequent side effects is minimal. The major risks associated with topical lidocaine administration are reactions locally at site of patch application, including blisters, bruising, burning sensation, depigmentation, dermatitis, discoloration, edema, erythema, exfoliation, irritation, papules, petechia, pruritus, vesicles, or abnormal sensation. The dose absorbed from the topical patches is small and so systemic adverse events are relatively unlikely. Systemic adverse effects, when they do occur, are expected to be similar in nature to those seen with other amide local anesthetic agents. This includes symptoms of central nervous system (CNS) excitation and/or depression, such as: light headedness, nervousness, apprehension, euphoria, confusion, dizziness, drowsiness, tinnitus, blurred or double vision, vomiting, sensations of heat, cold or numbness, twitching, tremor, convulsions, unconsciousness, respiratory depression, and arrest. Adverse events manifesting in the cardiovascular system may include bradycardia, hypotension, and cardiovascular collapse leading to arrest. Other miscellaneous adverse events that have been reported but causality has not been established include the following: asthenia, confusion, disorientation, dizziness, headache, hyperesthesia, hypoesthesia, lightheadedness, nausea, nervousness, exacerbation of pain, paresthesia, somnolence, taste alteration, vomiting, visual disturbances such as blurred vision, flushing, tinnitus, and tremor.

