#### **Additional risks include:**

The standard risks of injection, including reactions which may occur because of the injection, excipients or administration include fever, local tenderness, abscess, tissue necrosis or infection at the site of injection, venous thrombosis or inflammation of the vein (phlebitis). These risks will be minimized by employing the expertise of the Clinical Research Unit (CRU) nursing staff for administering the IV injection. The injection site will be monitored for signs of infection during the study to minimize this risk. The standard risks of phlebotomy and venipuncture, including discomfort upon placement of an IV catheter, will consist of bruising at the site of blood draw, hypersensitivity to adhesive plasters or surgical tape, irritation at the catheter site, as well as a small risk of infection. These risks will be minimized by using sterile technique, as well as employing the expertise of the experienced nursing staff of the CRU. The catheter site will be monitored for signs of infection during the study to minimize this risk.

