#### **5.3.3. Reasons for Withdrawal**

The primary reason for a subject's discontinuation should be selected from the following standard categories:

***Adverse Event (AE)*** – Clinical or laboratory events that in the judgment of the PI or MAI require discontinuation from the study in the best interest of subject. All AEs must have their relationship to the patch or IV injection assessed using the following terms: Associated or Not Associated. Upon occurrence of a Serious Adverse Event (SAE) possibly requiring discontinuation of a subject, the PI will confer with the ISM. If a subject is discontinued due to an AE, the event will be followed until it is adequately resolved.

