## APPENDIX C: TOXICITY GRADING SCALES

Vital Signs*	Reference Range of Normal Values	Mild (Grade 1)	Moderate (Grade 2)	Severe (Grade 3)	Potentially Life-Threatening (Grade 4)
Fever (°C)** (°F)	35-37.9 95-100.3	38.0-38.4 100.4-101.1	38.5- 38.9 101.2-102.0	39.0-40 102.1-104	>40 >104
Tachycardia - beats per minute	55-100	101-115	116-130	>130	ER visit or hospitalization for arrhythmia
Bradycardia - beats per minute	55-100	50- 54	45- 49	<45	ER visit or hospitalization for arrhythmia
Hypertension (systolic) - mm Hg	90 – 139	140 – 159	160 – 179	>180	ER visit or hospitalization for malignant hypertension
Hypertension (diastolic) - mm Hg	60 – 89	90 – 99	100 – 110	>110	ER visit or hospitalization for malignant hypertension
Hypotension (systolic) – mm Hg ***	90-139	85-89	80-84	< 80	Mean arterial pressure <60mm/ Hg or end organ damage or shock; requires hospitalization and vasopressor treatment
Respiratory Rate - breaths per minute	12-17	18-20	21- 25	>25	Intubation

\*Subject should be at rest for all vital sign measurements  
 \*\*Oral temperature; no recent (30 min) hot or cold beverages  
 \*\*\*A low diastolic blood pressure reading will be assessed to determine whether there are associated signs and symptoms

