**APPENDIX C: TOXICITY GRADING SCALE (CON'T)****TOXICOLOGY GRADING SCALE – SYSTEMIC**

	Grade 1	Grade 2	Grade 3	Grade 4
Allergic Reaction	Pruritus without rash	Localized urticaria	Generalized urticaria; angioedema	Anaphylaxis
Headache	Mild discomfort that is brief or easily tolerated	Discomfort that causes mild to moderate limitation in activity	Symptom prevents all normal activity for 24 hours or more	ER visit or hospitalization
Fatigue	Normal activity reduced	Normal activity decreased 25-0%	Can't go to work or school	ER visit or hospitalization
Any other illness or clinical adverse event	No interference with activity	Some interference with activity not requiring medical intervention	Prevents daily activity and requires medical intervention	ER visit or hospitalization

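### The graded halting limits in 9.5 count only known lidocaine side-effects, so non-serious Grade 3 events judged Associated with the patch or injection, but not known lidocaine effects, never trigger an automatic dosing halt.

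*Combined protocol and SAP*

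**What the plan says.** Section 9.5 lists three triggers for halting dosing pending ISM review:

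- "3 or more subjects develop Grade 2 or higher of the major side-effects known to be related to lidocaine";
- the same class of event at Grade 3 or above, in at least two subjects;
- any one SAE.

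The protocol does not define which side-effects are major. Section 9.2.3 lists expected local and systemic reactions and refers the reader to package inserts that are not among the documents.

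Causality is judged on a wider footing. Section 5.3.3 states: "All AEs must have their relationship to the patch or IV injection assessed using the following terms: Associated or Not Associated". The reference there is the product and its administration, not lidocaine alone.

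Section 2.3.1 sets out the lidocaine effects of the patches and of the injection. Under a separate heading for additional risks it then says that "reactions which may occur because of the injection, excipients or administration include fever", followed by local tenderness, abscess, tissue necrosis, infection and venous complications. Appendix C grades fever: Grade 3 is 39.0-40 °C and Grade 4 is above 40 °C.

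**The concern.** A study-level count is meant to catch a reaction that recurs across subjects, where each case alone looks manageable. A problem with the injection procedure, an excipient or a product lot would show itself in that way. Such a problem need not look like lidocaine toxicity, and the graded limits are confined to lidocaine toxicity. The judgement that would identify these events is already required for every AE, but the halting rule ignores it. At stake is the safety of subjects dosed after a cluster has begun. Nothing here touches the PK estimates.

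**Working it through.** The plan gives no operating characteristic for the halting rule, so there is no figure to reproduce. The check has two parts.

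**1. Applying the rule to an event the protocol foresees.** Suppose several subjects have a non-serious fever of 39.0-40 °C, judged Associated with the injection.

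| Question | Source | Answer |
|---|---|---|
| Foreseen? | 2.3.1, additional risks | Yes, as a reaction to the injection, excipients or administration |
| Graded? | Appendix C | Yes, Grade 3 |
| Named among the lidocaine effects? | 2.3.1 and 9.2.3 | No |
| Judged for causality? | 5.3.3 | Yes, Associated |
| Adds to the Grade 2 count? | 9.5, first limit | 0 |
| Adds to the Grade 3 count? | 9.5, second limit | 0 |
| Meets the SAE trigger? | 9.5 with 9.2.4 | No; Grade 4 reactogenicity is an SAE by definition, Grade 3 is not |

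The result is the same for two such subjects or for twenty. Abscess, tissue necrosis and infection at the injection site are in the same position: 2.3.1 names them and 9.2.3 does not.

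**2. How an extended Grade 3 limit would behave.** Inputs: n = 24 subjects (section 5), a limit of 2 subjects (9.5), and an assumed proportion p of subjects with at least one qualifying event. Each subject counts once, subjects are independent, and the count runs over the whole study. Then

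P(2 or more) = 1 − (1 − p)^24 − 24p(1 − p)^23

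- p = 1%: 1 − 0.7857 − 0.24 × 0.7936 = 0.024
- p = 2%: 1 − 0.6158 − 0.48 × 0.6284 = 0.083
- p = 5%: 1 − 0.2920 − 1.20 × 0.3074 = 0.339

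Section 5 also provides ten alternates. If all ten were dosed (n = 34), the same formula gives 0.045, 0.148 and 0.512. Under the present wording these events alone reach a graded limit with probability 0 at every p.

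**The case against.** The strongest reply is that these events are far from unwatched.

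- The ISM reviews all adverse effects (9.1), reviews AEs after each arm (9.5), and advises whether each subject goes on to the next arm (4, 9.6).
- The ISM must investigate unexpected serious events and take any event needing further evaluation to the FDA medical officer (9.6).
- Unexpected AEs, and expected ones that become more frequent than foreseen, go to the RIHSC within 7 working days (9.3.1).
- Moderate or worse AEs prompt laboratory tests that go to the MAI and ISM (8.2.1).
- A subject with a clinical problem is discontinued (9.4). Fever has its own holds in exclusion 5 of 5.2 and item 4 of 7.2.1.
- An event may be judged an SAE on medical grounds (9.2.4).

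All of this stands. A reader might infer that such reactions go unseen, or that the study could not be paused for them; the documents do not support that. But these provisions act on the individual subject, require reporting, or leave the decision to judgement. The ISM's stated power in 9.6 is to pause enrolment, whereas 9.5 halts dosing. None of them is a numeric trigger across subjects.

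A second reply is that the package inserts may name fever, and that the word major is undefined. That is fair, and it weakens fever as an example. It does not remove the restriction itself, which still excludes any Associated reaction outside known lidocaine effects. Headache would be a poor second example, because 2.3.1 already lists it among patch events with unsettled causality: "Other miscellaneous adverse events that have been reported but causality has not been established include the following: asthenia, confusion, disorientation, dizziness, headache".

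A third reply is that limiting the counts to known drug toxicity is defensible for marketed patches at approved dosing and one low-dose injection. At Grade 2 this reply carries weight. A reader might infer that the first limit should be widened too. If it were widened to unlisted Associated events, three subjects with three different minor events could halt dosing, while listed non-major reactions still would not. With 24 subjects the chance of 3 or more is 12% at an assumed 5% and 44% at 10%.

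**Conclusion.** The point holds in a narrow form. Both graded limits exclude non-serious Grade 3 events that are judged Associated but are not known lidocaine effects, so no number of them produces an automatic dosing halt. The gap is the missing study-level trigger; it is not a lack of oversight. It is a cheap improvement to consider, with no bearing on the PK results.

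The conclusion rests on the plain reading of 9.5, 2.3.1, 5.3.3 and Appendix C, and on the reaction lists as they stand without the package inserts. The 2%, 8% and 34% figures rest on assumed rates. They describe how the counter would behave and do not estimate risk in this trial.

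Two further changes might seem to follow, and neither is warranted. One is the wider Grade 2 limit discussed above. The other is an edit to the expectedness sentence in 9.2.3 that begins "If an event has not been experienced previously and is not listed here": the halting rule does not use that label, and changing it would alter which events are handled as unexpected elsewhere.

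**What to change.** Leave the first limit and the SAE trigger as they are. Extend the second limit so that it reads: "2 or more subjects develop Grade 3 or higher of the major side-effects known to be related to lidocaine", *or any AE of Grade 3 or higher assessed as Associated with the patch or IV injection*. Make clear that the two-subject threshold governs both parts, so that a single such AE does not halt dosing. Do not tie the added clause to the 9.2.3 list or to the package inserts, since their content would then decide what counts.

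The change needs one clause and no new data, because 5.3.3 already requires the judgement. Listed Grade 3 reactions that are Associated but not considered major would now count as well. Since 9.2.3 scores skin irritation on its own 0-4 scale, the amendment should say whether an irritation score of 3 is treated as a Grade 3 AE.

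The downside is an occasional extra review, with the probabilities shown above. Under 9.5 a halt leads to a decision by the PI, MAI and ISM on whether to continue, so the cost is a pause and not a stop.
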